5.5. Permanent Discontinuation of Randomized Treatment

Every effort should be made to keep subjects in the study including those who permanently stop randomized treatment. A subject may permanently discontinue randomized treatment at any time at his/her own request, or at the discretion of the investigator for safety or compliance reasons. A subject must permanently discontinue randomized treatment for the pre-specified reasons below.

- Kidney transplant
- Meets criterion to receive rescue (Section 6.12)
- Becomes pregnant or intends to become pregnant during the study.
- Liver chemistry abnormalities exceeding the threshold criteria (Section 7.4.12).
- Diagnosis of cancer (new or recurrent), with the exception of localized squamous cell or basal cell carcinoma of the skin.
- Need for more than 14 days use of prohibited medication (Section 6.10.2)

In all cases, the reason for randomized treatment discontinuation and the date of the last dose will be recorded in the subject's electronic case report form (eCRF) and the subject will continue in the study as described in Section 5.5.1.

Subjects may be reapproached about restarting randomized treatment in certain circumstances if the sponsor and the investigator agree.

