5.5.1. Procedures for Subject Follow-up

Subjects who permanently discontinue randomized treatment will be asked to attend an Early Treatment Discontinuation visit and will be expected to attend study visits through the End of Study visit, according to the study visit schedule, unless consent is actively withdrawn. Complete details are provided in the Time and Events Table (Section 7.1).

- Early Treatment Discontinuation visit: This visit should occur within 2 weeks of stopping randomized treatment.
- Remaining in-clinic visits*:
 - Day 1 through Week 52: Study visits at Weeks 4, 16, 28, 40 and 52.
 - Week 52 through end of study: Study visits every 12 weeks.
 - End of Study visit: as defined by the sponsor within a pre-defined time period.

*Phone visit acceptable in exceptional circumstances.

If a subject does not agree to continue attending in-clinic or phone visits, other follow-up options to collect study outcomes and vital status should be pursued according to local laws and regulations. If one of these alternate methods to collect study outcomes and vital status is acceptable to the subject, then the subject will be considered to have remained in the study and not to have withdrawn consent.

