Ferritin, total iron, UIBC, hepcidin, lipids, iPTH	X		
Hospitalization ¹ , kidney transplant ¹	X	X	X
Non-serious AEs, AEs of special interest, SAEs, clinical events	X	X	X
Review concomitant medications	X	X	X
Healthcare resource utilization (subject reported)	X		
PGI-S, PGI-C ^{4,9}	X		
SF-36 ^{4,9}	X		
EQ-5D-5L& EQ-VAS ^{4,5,9}	X		
ABPM sub-study (Appendix 12): 24 hour ABPM		X (Week 16)	
Record awake and sleep times		X (Week 16) ²	

Note: see footnotes on next page

Schedule of Assessments for Subjects Permanently Discontinuing Randomized Treatment (Continued)

Protocol activity (visits \pm 2 week) (Note: All visit timings are relative to Day 1)	Year 2 ⁷				Year 3 ⁷				Year 4 ⁷					Unscheduled	End of Study ⁸
	Week 64	Week 76	Week 88	Week 100	Week 112	Week 124	Week 136	Week 148	Week 160	Week 172	Week 184	Week 196	Week 208		
IRT system call															X
SBP/DBP, HR (pre- and post-dialysis for in-center HD subjects, between treatments for HHD and PD subjects) (single readings unless otherwise indicated)	X	X	X	X	X	X	X	X	X	X	X	X	X	X	X
HemoCue Hgb	X	X	X	X	X	X	X	X	X	X	X	X	X	X	X
Hematology ³	X	Hgb only	X	Hgb only	X	Hgb only	X	Hgb only	X	Hgb only	X	Hgb only	X		X
Clinical chemistry ³	X		X		X		X		X		X		X		X
Hospitalization ¹ , kidney transplant ¹	X	X	X	X	X	X	X	X	X	X	X	X	X	X	X
Non-serious AEs, SAEs, AEs of special interest, clinical events	X	X	X	X	X	X	X	X	X	X	X	X	X	X	X
Review concomitant medications	X	X	X	X	X	X	X	X	X	X	X	X	X	X	X

1. Record in eCRF, if applicable.

2. Subject will record sleep and wake time during the ABPM session.

3. See details on hematology and clinical chemistry in Section 7.4.11.

4. Only completed at Early Treatment Discontinuation visit if the randomized treatment discontinuation occurs on or before Week 52

5. Only in selected countries. See Appendix 3.

6. Additional pregnancy test required at subsequent visit. Must be at least 4 weeks after the end of randomized treatment.

7. Phone visits are acceptable in exceptional circumstances.

8. Investigator will inform subject when to attend this End of Study visit.

9. Subjects who are unable to or require assistance to read must not complete the questionnaires.

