9.4.2. Secondary Analyses

9.4.2.1. Principal Secondary Analyses

Conditional on the co-primary endpoints achieving at least non-inferiority at the one-sided 2.5% level, statistical testing will progress to superiority for MACE and the principal secondary endpoints. The hypotheses to be tested for these endpoints are as follows:

- **Null:** daprodustat is not superior to rhEPO (i.e. the hazard ratio is greater than or equal to 1.0 for time-to-event endpoints, or the mean difference is greater than or equal to 0 for continuous endpoints)
- **Alternative:** daprodustat is superior to rhEPO (i.e. the hazard ratio is less than 1.0 for time-to-event endpoints, or the mean difference is less than to 0 for continuous endpoints)

These tests will be multiplicity adjusted based on a family-wise Type I error rate set at the one-sided 2.5% level, see Section 9.4.3 for further details.

For “time to event” endpoints: The statistical modeling approach described for MACE in Section 9.4.1.1 will be repeated for the adjudicated composite endpoints of:

- MACE or a thromboembolic event (vascular access thrombosis, symptomatic deep vein thrombosis or symptomatic pulmonary embolism).
- MACE or hospitalization for HF.

For the average monthly IV iron dose up to Week 52 endpoint: IV iron use for all subjects will be recorded in the eCRF and the average monthly IV iron dose up to week 52 will be calculated. An ANCOVA model will be used to compare the difference in this average monthly IV iron dose per subject between arms, including factors for baseline dose, treatment and the prognostic randomization stratification factors.

Additional secondary endpoints are listed in [Appendix 2](#). All analyses of secondary endpoints are of exploratory nature, summary statistics and nominal one-sided p-values will be used for any treatment comparisons.

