12.2. Appendix 2: Secondary and Exploratory Objectives/ Endpoints

Objectives	Endpoints
Secondary Objectives	Secondary Endpoints (tested for superiority¹, no multiplicity adjustment)

 To compare daprodustat to rhEPO on additional CV safety endpoints 	
 All-cause mortality, CV mortality, fatal or non-fatal MI, fatal or non-fatal stroke² MACE or hospitalization for HF² (recurrent events analysis) CV mortality or non-fatal MI² All-cause hospitalization All cause hospital re-admission within 30 days MACE or hospitalization for HF or thromboembolic events² Hospitalization for HF² Thromboembolic events²

 To compare daprodustat to rhEPO on Hgb variability 	
 Hgb change from baseline to Week 52¹ N (%) responders, defined as mean Hgb within the Hgb analysis range 10-11.5 g/dL during EP % time Hgb in analysis range (10-11.5 g/dL) during the evaluation period (EP, Week 28 to 52) and during the maintenance period (MP; Week 28 to end of trial) (non-inferiority analysis that will use a margin of 15% less time in range)¹

 To compare daprodustat to rhEPO on BP 	
 Change from baseline in SBP, DBP and MAP at Week 52 and at end of treatment Number of BP exacerbation events per 100 patient years N (%) with at least one BP exacerbation event during study

 To compare daprodustat to rhEPO on the time to rescue (defined as permanently stopping randomized treatment due to meeting rescue criteria). 	
 Time to stopping randomized treatment due to meeting rescue criteria

 To compare daprodustat to rhEPO on HRQoL and Utility score 	
 Mean change in SF-36 HRQOL scores (Physical Component Score (PCS), Mental Component Score (MCS) and 8 health domains) between baseline and Weeks 8, 12, 28, 52, of particular interest are the changes from baseline in the vitality and physical functioning domains at Wk 28 and 52 Change from baseline in Health Utility (EQ-5D-5L) score at Week 52 Change from baseline in EQ VAS at Week 52

 To compare daprodustat to rhEPO on the symptom severity and change 	
 Change from Baseline at Wk 8, 12, 28, 52 in PGI-S

Objectives	Endpoints

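### Patient-reported outcomes are not scheduled at Weeks 28 and 52 for subjects who stopped randomized treatment earlier, although those subjects still attend both visits

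*Protocol*

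**What the plan says.** **Endpoints.** Protocol Appendix 2 lists the patient-reported outcomes (PROs) under "Secondary Endpoints (tested for superiority¹, no multiplicity adjustment". SF-36 is compared at Weeks 8, 12, 28 and 52, and "of particular interest are the changes from baseline in the vitality and physical functioning domains at Wk 28 and 52". The other entries include "Change from baseline in Health Utility (EQ-5D-5L) score at Week 52", the same for EQ VAS, and "Change from Baseline at Wk 8, 12, 28, 52 in PGI-S". Section 9.4.2.1 sets their status: "All analyses of secondary endpoints are of exploratory nature, summary statistics and nominal one-sided p-values will be used for any treatment comparisons".

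**Who leaves treatment but not the study.** Section 5.5 lists the reasons that force permanent discontinuation. One is "Meets criterion to receive rescue (Section 6.12"; others include kidney transplant, pregnancy, cancer and liver chemistry criteria. Subjects may also stop at their own request. All are asked to stay in follow-up. Section 5.5.1 gives their in-clinic schedule: "Day 1 through Week 52: Study visits at Weeks 4, 16, 28, 40 and 52".

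**What is collected from them.** Table 9 in Section 7.1 governs these subjects. PGI-S/PGI-C, SF-36 and EQ-5D-5L/EQ-VAS each have one mark, under the Early Treatment Discontinuation visit, with the footnote "Only completed at Early Treatment Discontinuation visit if the randomized treatment discontinuation occurs on or before Week 52". The column for Weeks 4, 16, 28, 40 and 52 has no PRO entry. It does have entries for Hgb, hematology, chemistry, blood pressure, iron therapy, events and, at Week 16, ambulatory blood pressure.

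**The concern.** A comparison at a fixed week describes the randomized groups only if outcomes are sought at that week from everyone still in follow-up. Here the schedule stops seeking them once a subject leaves randomized treatment. Inadequate responders leave by rule, through the rescue criterion, so the loss is tied to treatment response and is not incidental.

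The protocol itself treats time to stopping for rescue as a secondary superiority comparison. It thus allows that the arms may differ on the very event that ends PRO collection. If they do, the Week 28 and Week 52 PRO results compare differently selected groups.

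The hemoglobin co-primary counts values in Weeks 28 to 52 whether or not the subject discontinued or was rescued (Section 9.1.2). Hemoglobin and quality of life over the same period would then describe different populations. At stake is the reading of a nominal PRO difference at Week 28 or 52 as a comparison of randomized groups when it is closer to a comparison of subjects still on treatment.

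**Working it through.** No figure stated in the protocol depends on this point. It gives no sample size, SD or expected discontinuation rate for any PRO. The check is mainly of one schedule against another.

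**Step 1: do the cells really mean no collection?** Table 8, the general PRO schedule, is not expressly limited to subjects on treatment, so it might be thought to apply to everyone. Table 9, however, is the specific schedule for discontinued subjects, and it lists again the Table 8 items that are kept. Week 16 ambulatory monitoring appears in both tables, and Section 12.12.3.4 confirms that it is done off treatment. PROs are carried into Table 9 at the discontinuation visit alone. The consistent reading is that no PRO is scheduled afterwards.

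**Step 2: who is affected?**

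| Subject stops treatment | Week 28 PRO scheduled | Week 52 PRO scheduled |
|---|---|---|
| before Week 28 | no | no |
| between Weeks 28 and 52 | yes | no |
| after Week 52 | yes | yes |

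The loss at each week is confined to those who stopped before it.

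**Step 3: is there a visit at which to collect?** Yes at Weeks 28 and 52 (Section 5.5.1), and Section 7.7 has the questionnaires completed at clinic visits. Weeks 8 and 12 differ: Table 9 has no visit then.

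**Step 4: how many subjects?** Assumed share *d* stopped before Week 52, with about 3000 randomized, 1500 per arm (Section 4.2):

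- *d* = 10%: 3000 × 0.10 = 300 without a scheduled Week 52 PRO; 1500 × 0.90 = 1350 per arm remain
- *d* = 20%: 600 without; 1200 per arm remain
- *d* = 30%: 900 without; 1050 per arm remain

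This assumes equal rates in both arms, and is before deaths, other losses and, for EQ-5D-5L/EQ-VAS, the restriction to selected countries.

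**Step 5: how large a shift?** In each arm let *d* be the share off treatment and δ the mean outcome of those subjects minus that of continuers, in SD units with higher meaning better. The arm mean over all subjects is the continuer mean plus *d*δ, so

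all-randomized difference = on-treatment difference + (*d*δ for daprodustat) − (*d*δ for rhEPO).

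Set the on-treatment difference to 0. All inputs are assumed:

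- 20% off treatment in both arms, same δ: shift 0
- 15% v 25% (daprodustat v rhEPO), δ = −0.25 in both: −0.0375 + 0.0625 = 0.025 SD
- 15% v 25%, δ = −0.5 in both: −0.075 + 0.125 = 0.05 SD
- 20% v 30%: the same two results, 0.025 and 0.05 SD
- 20% in both arms, δ = −0.5 v −0.25: −0.10 + 0.05 = −0.05 SD

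The sign depends on which arm loses more subjects and on how they fare later. For scale, the 95% CI half-width with 1200 per arm is 1.96 × √(2/1200) = 0.08 SD.

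**The case against.** **These endpoints carry little weight.** Section 9.4.2.1 calls them exploratory, with nominal p-values. They lie outside the co-primaries and outside the Holm-Bonferroni family of Section 9.4.3. This stands: a reader should not infer that trial success or type I error is touched.

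**It may be a deliberate estimand.** After discontinuation, anemia treatment follows local practice, so later scores would partly reflect non-study therapy. One last assessment followed by none suits a while-on-treatment question, and the protocol plans an on-drug analysis for hemoglobin too. That is a legitimate question, but for hemoglobin it stands beside the treatment-policy analysis, and off-treatment values are collected to support both. For PROs the schedule closes off one of them, and the endpoint list does not say that the comparison is on-treatment.

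**It is easy to say too much here.** Four stronger readings are tempting and are not supported:

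- That everyone who was rescued or stopped is excluded. Step 2 shows that only those who stopped before the given week are.
- That footnote 4 itself ends collection. It only sets when the discontinuation-visit assessment is done; the gap comes from the empty cells.
- That the discontinuation-visit value cannot enter a Week 28 or Week 52 analysis. The visit falls within 2 weeks of stopping, so it may lie close to a nominal week. Section 9.4.2.2 leaves PRO analysis to the RAP, and no fault is alleged there.
- That the arm losing more poor responders is bound to look better. Discontinuation is also mandatory for transplant, after which quality of life could improve. Direction cannot be settled from the protocol.

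**The analysis plan could deal with it.** Only in part. It can choose windows and imputation, but it cannot supply observations that the schedule never asks for.

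**Conclusion.** The gap is real and is fixed by the protocol's own schedule. Subjects who permanently stop randomized treatment before Week 28 or Week 52, including all who meet the rescue criterion by then, have no scheduled PRO at that week despite an expected clinic visit. The Week 28 and Week 52 secondary PRO comparisons therefore rest essentially on on-treatment subjects.

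The bias may run in either direction and is nil if discontinuation and later outcomes match between arms. Its size is unknown, because the protocol states no rates. Under the assumed inputs above it is 0.025 to 0.05 SD in absolute value, less than the 0.08 SD half-width of the comparison, so probably modest. The difficulty is that without post-discontinuation values it cannot be checked. This is a worthwhile, cheap improvement to exploratory secondary endpoints and does not threaten the trial's primary conclusions.

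**What to change.** Add PGI-S, PGI-C, SF-36 and EQ-5D-5L/EQ-VAS to the Week 28 and Week 52 visits in Table 9, keeping the existing limits on countries and on subjects who need help to read. No new visit is required; the cost is a few minutes of each subject's time and a table amendment.

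Section 9.2.3 states that enrollment was complete at the current amendment, so some or many of these visits may have passed. For subjects already beyond them, state that the Week 28 and Week 52 PRO results are on-treatment comparisons. Add a sensitivity analysis in all randomized subjects that uses the values collected at the Early Treatment Discontinuation visit, for example by multiple imputation conditional on them. This needs no new data and costs one further analysis, but it rests on an untestable assumption about how scores move after that visit, so it is second best to collecting them.

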7.2. Screening and Critical Baseline Assessments

Before any study-specific procedure is performed, valid informed consent must be obtained at screening.

Demography and medical history (including CV medical history/risk factors) will be assessed at screening (Week -8).

Randomization requires a Hgb on Day 1 in the range as defined by ESA use and region (Section 4.1).

Full details of screening (Week -8) and baseline (Day 1) assessments are provided in the Time and Events Table Section 7.1.

7.3. Efficacy

Planned time points for all Hgb efficacy assessments are listed in the Time and Events Table (Section 7.1).

GSK will supply a point-of-care Hgb analyzer (i.e., HemoCue) to each site for rapid measurement of Hgb.

Blood samples for measurement of Hgb via HemoCue and also by the central laboratory will be collected as specified in Time and Events Table (Section 7.1).

7.4. Safety

Planned time points for all study safety assessments are listed in the Time and Events Tables (Section 7.1). Unscheduled visits will occur as medically necessary. Detailed procedures for obtaining each assessment are provided in the SRM.

Safety endpoints will include monitoring of safety endpoint events including deaths (Section 7.4.1), other CV events (Section 7.4.2), AEs of special interest (Section 7.4.4), AEs, SAEs and AEs leading to discontinuation of randomized treatment, laboratory parameters, BP and HR.

Pre-specified events leading to permanent discontinuation of randomized treatment are described in Section 5.5. Liver chemistry stopping and follow-up criteria are described in Section 7.4.12 and Appendix 8.

7.4.1. Events Referred to the Clinical Events Committee

Investigators should refer any event suspected to be one of the events below to the Clinical Events Committee for adjudication. See CEC Site Manual for full scope of reporting requirements.

- All-cause mortality (CV and non-CV mortality)
- Non-fatal MI

- Non-fatal stroke
- Hospitalization for HF
- Thromboembolic events (vascular access thrombosis, deep vein thrombosis, pulmonary embolism)

When the investigator-reported event and the Clinical Events Classification (CEC) assessment by the committee differ, the committee's decision will be considered final. The detailed descriptions of the endpoint definitions used for adjudication are contained within the Clinical Events Committee Charter (available on request).

Source documentation required to support the adjudication of the events is described in the CEC Site Manual. Recording of potential endpoint events in the eCRF and submission of source documentation will be required.

Positively adjudicated events will be reported separately (Section 7.4.3). Negatively adjudicated events will be reported as AEs or SAEs using the investigator-reported event term.

7.4.2. Other CV Events

GSK has identified other CV events of interest for all clinical studies. Investigators will be required to fill out the specific CV event page of the eCRF for the following CV AEs and SAEs or any event that may potentially be one of the categories listed:

- Arrhythmias
- Pulmonary hypertension (also an AE of special interest see Section 7.4.4 for further details).
- Valvulopathy
- Revascularization

7.4.3. Adverse Events (AE) and Serious Adverse Events (SAEs)

The definitions of an AE or SAE can be found in [Appendix 7](#).

The investigator or their designees are responsible for detecting, documenting and reporting events that meet the definition of an AE or SAE.

For this study, events referred to the Clinical Events Committee (Section 7.4.1) will be subjected to blinded adjudication using pre-specified diagnostic criteria. Positively adjudicated events will be reported separately. Negatively adjudicated events will be reported as AEs or SAEs using the investigator-reported event term.

Events should be reported as an AE or SAE according to the definitions in [Appendix 7](#).

7.4.3.1. Time period and Frequency for collecting AE and SAE information

- Any SAEs assessed as related to study participation (e.g., protocol-mandated procedures, invasive tests, or change in existing therapy) or related to a GSK product will be recorded in the subject's eCRF from the time a subject consents to participate in the study up to and including any follow-up contact.
- AEs and SAEs will be collected from the start of placebo run-in until the Follow-up visit (or the "End of Study" visit for subjects that discontinue study treatment early) (Section 7.4.3.2), at the time points specified in the Time and Events Table (Section 7.1).
- Medical occurrences that begin prior to the start of placebo run-in but after obtaining informed consent may be recorded on the Medical History/Current Medical Conditions Section of the eCRF.
- All SAEs will be recorded in the eCRF and reported to PPD within 24 hours, as indicated in [Appendix 7](#).
- Investigators are not obligated to actively seek AEs or SAEs in former study subjects. However, if the investigator learns of any SAE, including a death, at any time after a subject has been discharged from the study, and he/she considers the event reasonably related to the randomized treatment or study participation, the investigator must promptly notify PPD.

NOTE: The method of recording, evaluating and assessing causality of AEs and SAEs plus procedures for completing and transmitting SAE reports to PPD are provided in [Appendix 7](#).

7.4.3.2. Method of Detecting AEs and SAEs

Care will be taken not to introduce bias when detecting AEs and/or SAEs. Open-ended and non-leading verbal questioning of the subject is the preferred method to inquire about AE occurrence. Appropriate questions include:

- "How are you feeling?"
- "Have you had any (other) medical problems since your last visit/contact?"
- "Have you taken any new medicines, other than those provided in this study, since your last visit/contact?"

7.4.3.3. Follow-up of AEs and SAEs

After the initial AE/SAE report, the investigator is required to proactively follow each subject at subsequent visits/contacts. All endpoint events (as defined in Section 7.4.1), SAEs, and non-serious AEs of special interest (as defined in Section 7.4.4) will be followed until resolution, until the condition stabilizes, until the event is otherwise explained, or until the subject is lost to follow-up (as defined in Section 5.5). Further information on follow-up procedures is given in [Appendix 7](#).

